4.4.1.9. Quality of Life Outcomes Related to Radiation Treatment

All patients will be given quality of life and symptom monitoring questionnaires including AUA symptom score sheet and the SHIM score sheet. The questionnaries will be given at the radiation consult visit and at follow up visits as part of the standard of care treatment.

4.4.2 SURGICAL PROCEDURES

4.4.2.1 Gold fiducial marker placement.

Gold seeds will be placed under ultrasound guidance in the prostate of patients as fiducial markers for radiation therapy prior to commencement of EBRT. Fiducial marker placement is standard of care for patients undergoing EBRT and will be performed following standard techniques.

4.4.2.2. Prostate biopsies.

Standard 12-core biopsies for diagnosis will be performed under transrectal ultrasound (TRUS) guidance at study entry on subjects who have not yet undergone diagnostic biopsy for prostate cancer. At the same time, up to 6 additional targeted core biopsy research samples will be obtained for purposes of the correlative studies described in Section 9.0. Subjects who have already undergone diagnostic prostate biopsies at the time of screening will undergo repeat

TRUS-guided biopsy to obtain up to 6 core biopsy samples for correlative studies at the time of study enrollment. TRUS-guided biopsy is performed as standard of care for the diagnosis and risk-stratification of patients with prostate cancer. A second set of up to -6 targeted research biopsy samples will be obtained under TRUS-guidance at the time of gold seed fiducial marker placement in all subjects enrolled in the study.

Biopsies will be formed using the Koelis Urostation with PROMAP-MR software. This approved, commercially available imaging and biopsy technology permits 3-dimensional transrectal ultrasound and MRI fusion to target tumor tissue within the prostate for biopsy, and will permit repeat biopsy of the same sites. The Urostation is a mobile software platform which can improve the prostate biopsy procedure with 3D imaging and image fusion capabilities. The Urostation connects to an ultrasound scanner equipped with a 3D transrectal probe. It receives stores and processes 3D Dicom images of the prostate as the physician performs the biopsy procedure. Organ-Based Tracking is an automatic 3DTRUS/3DTRUS registration based on the organ position within the image. This registration is robust to prostate and patient motion. The MRI/3DTRUS fusion is elastic since prostate deformation is corrected for optimal precision using a morphological contouring method. One significant advantage of this system is allowing mapping of biopsies as the Urostation guides and records each biopsy. It also allows real-time feedback on the targeted prostate region with an overlay of prior biopsy locations so a rebiopsy can be performed accurately of the region of interest.

4.5 Duration of Therapy

In the absence of treatment delays due to adverse events, treatment may continue for up to 36 months or until:

- Disease progression
- Inter-current illness that prevents further administration of treatment
- Unacceptable adverse event(s)
- Subject decides to withdraw from the study, OR
- General or specific changes in the patient's condition render the subject unacceptable for further treatment in the judgment of the investigator".

4.6 Duration of Follow Up

Subjects will be followed for **12 months after initiation of treatment** with enzalutamide plus GnRH agonist or until death, whichever occurs first. Subjects removed from treatment for unacceptable adverse events will be followed until resolution or stabilization of the adverse event. Subjects will be followed at monthly (every 28 +/- 3 days) visits for 12 months from the time of initiation of treatment with enzalutamide plus GnRH agonist. Total treatment will be for up to 36 months. The frequency of the follow up visits will be at the discretion of the investigator up to 36 months. The duration of treatment with the study agent enazalutamide will be for the initial 6 months, and follow up on study will continue for an additional 6 months following completion of enzalutamide.

4.7 Removal of Subjects from Protocol Therapy

Subjects will be removed from therapy when any of the criteria listed in Section 5.5 apply. Notify the Principal Investigator, and document the reason for study removal and the date the subject was removed in the Case Report Form. The subject should be followed-up per protocol.

4.8 Subject Replacement

If a subject is withdrawn from the study prior to the initiation of radiation therapy for reasons other than AEs as outlined in tables 4.2.1 and 4.2.2, an additional subject may be added to the study.

5.0 STUDY PROCEDURES

5.1 Screening/Baseline Procedures

Assessments performed exclusively to determine eligibility for this study will be done only after obtaining informed consent. Assessments performed for clinical indications (not exclusively to determine study eligibility) may be used for baseline values even if the studies were done before informed consent was obtained.

All screening procedures with the exception of a bone scan, must be performed within - 56 days prior to registration unless otherwise stated. A bone scan must be performed within – 90 days prior to registration. The screening procedures include:

5.1.1 Informed Consent

5.1.2 Medical history

Complete medical and surgical history, history of infections

5.1.3 Demographics

Age, gender, race, ethnicity

5.1.4 Review subject eligibility criteria

5.1.5 Review previous and concomitant medications

5.1.6 Physical exam including vital signs, height and weight

Vital signs (temperature, pulse, respirations, blood pressure), height, weight

5.1.7 *Performance status*

Performance status evaluated prior to study entry .

5.1.8 Adverse event assessment

Baseline adverse events will be assessed. See section 6 for Adverse Event monitoring and reporting.

5.1.9 Hematology

5.1.10 Blood draw for baseline blood counts, serum chemistries, PSA, and testosterone:

Complete blood count with automated or manual differential. Comprehensive metabolic panel (CMP) to include: albumin, alkaline phosphatase, ALT/SGPT, AST/SGOT, BUN, creatinine, electrolytes (sodium, potassium, calcium, chloride, bicarbonate), glucose, and total bilirubin. PSA. Serum total testosterone.

5.1.11 Tumor assessment and imaging

5.1.12.1 For patients with prostatic adenocarcinoma histologically confirmed prostatic adenocarcinoma, imaging assessment will include CT of the abdomen and pelvis OR pelvic MRI; PA/lateral chest x-ray OR chest CT; and bone scan. CT, MRI, and CXR must be performed within 56 days of enrollment. Bone scan must be performed within 90 days of enrollment. At enrollment, these subjects will undergo a research MRI of the prostate with TRUS-guided targeted prostate tumor biopsies. For patients who have not yet undergone CT abdomen/pelvis or MRI of the pelvis but are otherwise eligible for the trial, the

mandated research sequences from the prostate MRI may be obtained concurrently with the required standard of care MRI.

5.1.12.2 For subjects who have not yet undergone diagnostic prostate biopsies to confirm the presence of prostatic adenocarcinoma at the time of study enrollment, but who otherwise meet eligibility criteria (as defined in section 3.1.1: serum PSA > 20 ng/dL and/or clinical T3 disease by digital rectal exam), standard of care diagnostic and research biopsies of the prostate will be performed simultaneously under ultrasound guidance. Subjects will undergo MRI of the pelvis, bone scan, and CXR (PA and lateral)or chest CT at enrollment. MRI of the pelvis must be performed prior to prostate biopsy.

5.2 Procedures During Treatment

Subjects will receive treatment in the following phases:

- Neo-adjuvant: Subjects will receive treatment with enzalutamide plus GnRH agonist for 8-10 weeks prior to the initiation of EBRT
- Concurrent: Subjects will continue to receive treatment with enzalutamide plus GnRH agonist for the duration of EBRT (8-10 weeks)
- Adjuvant: Subjects will receive treatment with enzalutamide plus GnRH agonist following completion of EBRT until a total duration of 24 weeks of enzalutamide plus GnRH agonist treatment has been completed
- Maintenance: Subjects will continue to receive GnRH agonist therapy following completion of treatment with enzalutamide to achieve a total of 24 - 36 months of GnRH agonist treatment.
- During the neo-adjuvant, concurrent, and adjuvant phases, subjects will receive treatment with enzalutamide plus GnRH agonist therapy for six 28 day cycles for a total duration of 24 weeks.

5.2.1 Prior to Each Treatment Cycle During Neo-Adjuvant, Concurrent, and Adjuvant phases (weeks 1-24):

- Physical exam, vital signs
- Hematology
- Serum chemistries
- Toxicity evaluation

5.2.2 Day – 56 to – 14:

- Procedure:
- o MRI pelvis
- TRUS-guided prostate biopsies

5.2.3 Weeks 7-11

- MRI pelvis
- Fiducial marker placement and TRUS-guided targeted prostate biopsies

5.2.4 Every 4 weeks during weeks 28-48 of Maintenance Phase:

- Physical exam, vital signs
- Hematology
- Chemistries
- Toxicity evaluation

5.2.5 Every 8 weeks during weeks 1-48:

• PSA, testosterone

5.3 Follow-up Procedures

Subjects will be followed every 4 weeks(+/- 3 days) after completion of (or early withdrawal from) study treatment until 48 weeks (12 months) after initiation of enzalutamide plus GnRH agonist. Following completion of the study, subjects will continue with maintenance therapy with GnRH agonist for up to 36 months total treatment time as standard of care and will be monitored at the discretion of the treating provider according to standard of care.

5.4 Time and Events Table

	Pre-study Days -56 to - 14	Day 1	Every 4 weeks (weeks 4- 48)	Every 8 Weeks (weeks 8-48)	Weeks 8- 10	End of study visit
Assessment						
Informed Consent	Х					
History and PE	Х	Х	Х			Х
Performance Status	Х	Х	X			Х
Toxicity Evaluations		Х	X			Х
CBC	Х	Χ*	Х			
СМР	Х	X*	Х			
PSA, testosterone	Х	Х*		X		
CXR PA/lateral or CT chest	Х					
Bone scan	X#					
CT abd and pelvis	x					
MRI pelvis	Х				Х	
TRUS-guided prostate biopsy	Х				Х	

*These tests will be repeated at day 1 if the pre-screening tests were done greater than 28 days before Day 1.

Bone scan will be performed during pre-study days – 90 to – 14.

5.5 Removal of Subjects from Study

Subjects can be taken off the study treatment and/or study at any time at their own request, or they may be withdrawn at the discretion of the investigator for safety, behavioral or administrative reasons. The reason(s) for discontinuation will be documented and may include:

- 5.5.1 Subject voluntarily withdraws from treatment (follow-up permitted);
- 5.5.2 Subject withdraws consent (termination of treatment and follow-up);
- 5.5.3 Subject is unable to comply with protocol requirements;
- 5.5.4 Subject demonstrates disease progression (unless continued treatment with study drug is deemed appropriate at the discretion of the investigator);

- 5.5.5 Subject experiences toxicity that makes continuation in the protocol unsafe;
- 5.5.6 Treating physician judges continuation on the study would not be in the subject's best interest;
- 5.5.8 Development of second malignancy (except for basal cell carcinoma or squamous cell carcinoma of the skin) that requires treatment, which would interfere with this study;
- 5.5.9 Lost to follow-up. If a research subject cannot be located to document survival after a period of 12 months, the subject may be considered "lost to follow-up." All attempts to contact the subject during the 12 months must be documented and approved by the Data Monitoring Committee.

6.0 Measurement of Effect

6.1 Antitumor Effect- Solid Tumors

Patients with high-risk localized or locally-advanced prostate cancer are eligible for enrollment in this study. Patients with high-risk localized prostate cancer by definition will not have measurable disease by RECIST. Patients also may have radiographic evidence of metastasis in regional lymph nodes (N1 disease as defined by the National Comprehensive Cancer Network Prostate Cancer Guideline Verson 3.2012) at the discretion of the treating physicians, if regional lymph nodes can be included in the planned radiation field. RECIST will not be used to monitor these regional lymph nodes for treatment response. Rather, in all patients, treatment response will be monitored by serum prostate specific antigen (PSA). The PSA nadir with EBRT combined with androgen deprivation therapy is known to vary. Following RTOG-ASTRO Phoenix Consensus, a PSA rise by 2 ng/mL or more above the nadir PSA is the standard definition for biochemical failure after EBRT with or without ADT. As the primary endpoint of this study is safety and tolerability as measured up to 12 months following initiation of combined enzalutamide and GnRH agonist therapy, it is expected that subjects will remain under treatment with maintenance GnRH agonist therapy at the completion of their time on study. Consequently, it is anticipated that subjects will not experience a PSA rise suggestive of disease progression as defined by RTOG-ASTRO Phoenix Consensus during the study enrollment period. Should subjects experience any PSA rise on 2 or more consecutive measurements while enrolled in the study, this will be considered evidence of disease progression. Subjects will undergo research MRI of the pelvis to quantify local response following 8 weeks of combined enzalutamide plus GnRH agonist treatment for research purposes.

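### Section 6.1 gives disease progression two unreconciled PSA definitions; the one without a size limit can be met by measurement fluctuation, and Sections 4.5, 4.7 and 5.5 disagree on what then follows

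*Combined protocol and SAP*

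**What the plan says.** Section 6.1 makes serum PSA the response measure in all patients. It notes that the nadir varies and states that "a PSA rise by 2 ng/mL or more above the nadir PSA is the standard definition for biochemical failure after EBRT with or without ADT". Because subjects should still be on GnRH agonist when they leave the study, it adds that "it is anticipated that subjects will not experience a PSA rise suggestive of disease progression as defined by RTOG-ASTRO Phoenix Consensus". The next sentence sets another criterion, that if subjects have "any PSA rise on 2 or more consecutive measurements while enrolled in the study, this will be considered evidence of disease progression". No size, reference value, detection limit or confirmation is attached to it.

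The consequence of progression appears in three places:

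- **Section 4.5:** "treatment may continue for up to 36 months or until" one of a list of events occurs. Disease progression is the first, without exception.
- **Section 4.7:** removal from therapy is worded as mandatory once any criterion in Section 5.5 applies.
- **Section 5.5:** withdrawal is worded as permitted, and item 5.5.4 reads "Subject demonstrates disease progression (unless continued treatment with study drug is deemed appropriate at the discretion of the investigator".

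PSA and testosterone are drawn every 8 weeks (Section 5.2.5; weeks 8 to 48 in the Section 5.4 table).

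**The concern.** Adjacent sentences use the same term for two different events. A sequence of 0.10, 0.11 and 0.12 ng/mL is progression under the second criterion. The cited definition would need a rise 100 times larger (2.00 against 0.02 ng/mL). A patient whose PSA is suppressed and stable could therefore be labelled as progressed because of assay variation. The label is also an input to provisions on stopping treatment, and those provisions do not agree on whether stopping is required. At stake are a PSA response description that two readers could complete differently, and possible changes to the regimen while its safety is being measured.

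**Working it through.** The plan gives no error rate for the PSA rule, so there is no figure to reproduce. The check asks how often the rule is met when nothing is changing.

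**Inputs from the protocol**

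- PSA draws at weeks 8, 16, 24, 32, 40 and 48 (5.2.5, 5.4).
- Enzalutamide for 24 weeks, with EBRT starting after 8-10 weeks (5.2).
- EBRT of 79.2 Gy at 1.8 Gy per fraction (4.4.1.5.1): 79.2/1.8 = 44 fractions; at an assumed five per week, 44/5 = 8.8 weeks. EBRT therefore ends at about week 17-19.
- Seven subjects in the Study Summary; Section 10.2 gives both ten and seven.

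**Assumptions, not in the documents**

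- A flat PSA with independent errors.
- A CV of 5% or 10%.
- Results reported to 0.01 ng/mL.
- Plateau levels of 0.02 to 0.3 ng/mL.

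**Step 1: untied values.** Any three values are in ascending order with probability 1/6.

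- Four values (weeks 24-48) contain two overlapping triples. They are both ascending with probability 1/24, so the risk is 1/6 + 1/6 - 1/24 = 7/24 = 29%.
- Five values (weeks 16-48): 3/6 - (1/24 + 1/24 + 1/120) + 1/120 = 50/120 = 42%.

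The wording could also mean two consecutive values above the running nadir. Enumerating the orderings on that reading gives 14/24 = 58% for four values and 94/120 = 78% for five.

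**Step 2: rounding.** Ties lower the risk. At 0.1 ng/mL and 5% CV the SD is 0.005. Reported values of 0.09, 0.10 and 0.11 then have probabilities of about 0.157, 0.683 and 0.157. One triple is 0.157 x 0.683 x 0.157 = 0.017. Two triples, with small tail terms added, give about 3.5%. The full calculation for four values gives:

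| True PSA (ng/mL) | Per patient, 5% CV | Per patient, 10% CV |
|---|---|---|
| 0.02 | about 0% | about 0% |
| 0.05 | 0.1% | 3.5% |
| 0.1 | 3.5% | 11% |
| 0.3 | 16% | 22% |

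**Step 3: any of seven patients**, 1 - (1 - p)^7, if all seven sat at the same level. At 0.1 ng/mL this is 22% (5% CV) to 57% (10% CV). At 0.3 ng/mL it is 71% to 83%.

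**Step 4: dependence on the plateau.** If PSA instead falls 10% per draw (assumption), the 10% CV risks drop to 0.3% at 0.1 and 1.4% at 0.3 ng/mL. Results that all lie below the reporting limit cannot rise, so the risk is then near zero.

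**Step 5: timing.** Two successive rises need three values. A plateau starting at week 8, 16 or 24 allows a chance trigger no earlier than week 24, 32 or 40. EBRT is complete by then, and enzalutamide is at or past its end.

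**The case against.** The second criterion can be read as deliberate. Section 6.1 offers nadir + 2 ng/mL as the general standard, says it is not expected to occur under continuing GnRH agonist, and then adds a more sensitive on-study signal. That is plausible, so the two sentences need not be called a contradiction. But the protocol does not say so, and a deliberately sensitive rule would still need a reference value and a way to treat trivial or unreportable changes.

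A reader might infer that false progression would take patients out of the 12-month safety assessment. The documents do not support that. Section 4.7 keeps removed subjects in follow-up, Section 5.3 continues four-weekly visits to week 48 after early withdrawal, Section 4.6 follows subjects for 12 months or until death, and Section 6.2 analyses everyone who took at least one dose. The halting rules in 7.7 and 10.1 count AE withdrawals (10.1 also SAEs), not progression.

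Nor is the PSA endpoint affected. Sections 2.3 and 10.3 define it before radiation, after two months of treatment, when only one post-baseline value is scheduled. A reader might also infer that noise would force removal from enzalutamide or EBRT. The timing above makes that unlikely, and 5.5.4 lets the investigator continue study drug.

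Finally, the size of the risk rests on assumptions about nadir and assay, and its range starts at about zero. All of these limits stand. They narrow the harm, but they do not remove the two definitions or the disagreement among 4.5, 4.7 and 5.5.

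**Conclusion.** The point holds as a problem of definition and consistency. Followed as written, the any-rise rule can label a stable, suppressed PSA as progressed. On a flat plateau with independent error the risk per patient is 29% (four values) to 42% (five values) without ties. With rounding to 0.01 ng/mL it runs from about 0% to 22% over the levels and CVs examined with four values. These are illustrations under assumed nadir and precision, not predictions for this cohort.

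The practical reach is GnRH agonist maintenance between about week 24 and week 48, which lies inside the 12-month safety period, and the descriptive PSA response label. With seven subjects, one mislabelled patient is 1/7 = 14% of the cohort. The documents do not support a stronger conclusion about the primary endpoint. The correction is worth making because it is cheap and removes conflicting instructions.

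**What to change.** In Section 6.1, the sponsor should reconcile the two definitions and state one explicit PSA progression rule: the reference value, the size of change, the handling of results at or below the detection limit, whether confirmation is needed, and whether the wording means successive rises or successive values above nadir. If a separate, more sensitive on-study signal is intended, 6.1 should say so and give it its own name.

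Sections 4.5, 4.7 and 5.5.4 should be reconciled on what follows from progression, including whether the investigator's discretion applies throughout. The clinical threshold and the stopping rule are for the sponsor to decide.

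For reporting, PSA rises may also be listed descriptively for each patient against the definition already cited, beside the testosterone drawn at the same visit. The cost is a wording amendment with IRB approval; no new samples or visits are needed.

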6.1.1 Definitions

Evaluable for toxicity. All subjects will be evaluable for toxicity from the time of their first treatment with study drug.

6.1.2 Methods for Evaluation of Measurable Disease: Magnetic Resonance Imaging (MRI) of the prostate and pelvis

6.1.2.1 Patient preparation

The participants will undergo prostate MRI following the standard institutional procedure. If patients have had prostate biopsies, a minimum of 3 weeks is recommended between the date of the MRI exam and the previous biopsy to reduce the influence of post-biopsy changes in diagnostic accuracy.¹⁵ Patients will be asked to refrain from ejaculation for 3 days preceding the examination to maximize distention of the seminal vesicle.¹⁶

6.1.2.2 Image acquisition

Patients will undergo an MR examination with our routine clinical protocol using a 3T MRI system (Philips Medical Systems, Cleveland, OH) and a pelvic phasedarray coil. Endorectal coil will not be used. The patient is imaged in the supine position and artifacts due to bowel peristalsis are minimized with sublingual administration of 0.250 mg of hyoscyamine sulfate (Levsin). Our protocol includes T2-weighted fast spin-echo images in the transverse, sagittal, and coronal planes; axial diffusion-weighted transverse single shot echo planar image (with ADC map); T1-weighted gradient-echo images acquired before, during, and following the intravenous injection of a single dose of a gadolinium-based contrast as it is done for our clinical prostate MRI protocol. Additional pulse sequences such as arterial spin labeling (ASL), blood oxygen level dependent (BOLD), and others might be incorporated into the MRI protocol for additional research purposes; the total examination time will not exceed 1.5 hours and the amount of intravenous contrast administered will be similar to the dose given for clinical prostate MRI examinations. If at any point during the study the participant indicates a desire to withdraw, the exam will be interrupted.

6.1.2.3 Potential risks associated with MRI

Patients will be screened for MRI contraindications and these will be exclusion criteria for this study. Safety rules will be strictly enforced and followed by the research study team, MRI technologists, and the study subjects themselves. During the MRI scanning process, the study team is in constant two-way communication with the participant and can remove him from the magnet immediately as needed. The MRI personnel are trained to respond to emergency situations, further supported by an institutional Rapid Response Team should an adverse event arise during the study visit. Standard radiofrequency coils provided by manufacturers of MRI machines will be used in this study. The risks associated with the use of these coils are minimal. However, with any RF coil, there is a small risk of skin burns if the coil is used improperly or is malfunctioning. The MRI staff at UT Southwestern Medical Center is fully trained in the proper use of these devices.

Subjects will be screened for renal impairment prior to administration of gadolinium-based contrast agents as it is routinely done in the Radiology Department at UT Southwestern. A serum creatinine determination within 30 days prior to the research MRI examination must be available to calculate an estimated glomerular filtration rate (eGFR). An eGFR calculation may be repeated closer to the MRI appointment if the patient's medical condition has changed. An eGFR ≥45 mL/min/1.73m2 is considered acceptable for administration of a standard weight-based dose of intravenous contrast for research purposes.¹⁷

We do not anticipate significant psychological stress related to this study procedure. Patients will be able to refuse to answer any of the questions, take a break or stop their participation in this study at any time.

